Part A			Part B		
Baseline (4 weeks)	GNX Titration (4 weeks)	GNX Maintenance (8 weeks)	Open-Label Extension (OLE) Available to patients who respond to GNX as defined per protocol	GNX Taper (2 weeks)	Safety Follow up Visit (2 weeks post taper)
Baseline Period	Treatment Period			OLE Period	
Screening Visit	Baseline Treatment Visit		2 week taper upon GNX discontinuation		2 week taper upon GNX discontinuation

GNX = ganaxolone

During the screening visit, each patient's baseline [REDACTED], will be collected and analyzed for post-study evaluation.

Patient rescreening is allowed as agreed by the sponsor and the investigator unless there is a general concern for patient safety or an inability for the patient to become eligible (e.g., GNX allergy, sensitivity or exposure, non-TSC and/or other ineligible epilepsy, chronic prohibited medical condition or treatment). Subsequent screening should take place at least 30 days from the patient's last visit, unless otherwise noted.

Part A includes a 4-week baseline and 4 weeks of investigational product (IP) titration followed by 8 weeks of dose maintenance followed by 2-week taper for those patients not continuing into the Part B OLE period. After meeting all eligibility criteria, approximately 30 patients aged 2 to 65 years (inclusive) with TSC-related epilepsy will be enrolled to receive GNX for a total of 12 weeks (4-week titration, 8-week maintenance) in addition to their standard anti-seizure medication(s) (ASMs). Patients will be titrated to 63 mg/kg/day (maximum 1800 mg/day) over 4 weeks, and then maintained at that dose for another 8 weeks. Patients who are not able to tolerate 63 mg/kg/day (or maximum 1800 mg/day) may be maintained on a lower dose after discussion with the sponsor medical monitor. A minimum dose of 33 mg/kg/day or 900 mg/day is generally required during the maintenance period.

For Part A, dose changes including alternative dosing paradigm (e.g., lower dose during the daytime and higher dose in the evening) should be discussed with the sponsor medical monitor prior to making the change or within 48 hours of making the change. Patients who discontinue GNX should undergo a 2-week taper period, unless otherwise medically indicated. Patients who discontinue GNX before the completion of the maintenance period

IND 044,020
Protocol 1042-TSC-2001Marinus Pharmaceuticals, Inc.
11 Jun 2021

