5. Have at least 8 countable/witnessed primary seizures during the 4-week baseline period with at least 1 primary seizure occurring in at least 3 of the 4 weeks of baseline. The primary seizure types are defined as the following: focal motor seizures without impairment of consciousness or awareness, focal seizures with impairment of consciousness or awareness, focal seizures evolving to bilateral, tonic-clonic convulsive seizures, and generalized motor seizures including tonic-clonic, bilateral tonic, bilateral clonic, or atonic/drop seizures. Focal aware non-motor and generalized seizures without motor features, infantile or epileptic spasms, and myoclonic seizures do not count as the primary seizure types.
6. Patient must be approved to participate by the sponsor or its designee (e.g., Epilepsy Consortium) after review of medical history, genetic testing, and patients' seizure types.

7. Patients should be on a stable regimen of ASMs at therapeutic doses for \geq 1 month prior to the screening visit, without a foreseeable change in dosing for the duration of Part A. Vagus nerve stimulator (VNS), ketogenic diet, and modified Atkins diet should be unchanged for 3 months prior to screening and will not count towards the number of ASMs.
8. Patients with surgically implanted VNS will be allowed to enter the study provided that all of the following conditions are met:
 - a. The VNS has been in place for \geq 1 year prior to the screening visit.
 - b. The settings must have remained constant for 3 months prior to the screening visit and remain constant throughout the baseline and Part A.
 - c. The battery is expected to last for the duration of baseline and Part A.
9. Parent/caregiver is able and willing to maintain an accurate and complete daily seizure diary for the duration of the study.
10. Able and willing to take IP (suspension) with food 3 times daily. (GNX must be administered with food).

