7.2. Study Procedures (Part A: Treatment Period)

7.2.1. Screening Period

7.2.1.1. Screening (Visit 1, Week -4)

Additional procedures/assessments to be completed during the screening period may include the following:

- Informed consent from parent/LAR (or patient assent)
- Demographics and medical history
- Review of inclusion/exclusion criteria
- Review previous genetic testing results to evaluate pathogenic or likely pathogenic *TSC1* or *TSC2* variant. If genetic testing has not previously been performed, then a biological sample will be obtained to complete genetic testing at the sponsor's designated lab.
Note: Tuberous Sclerosis Complex diagnosis does not require pathogenic *TSC1* or *TSC2* mutations if the clinical criteria are met.
- Seizure Identification and Diagnostic Review Form (SIF/DRF) (Epilepsy Study Consortium)

- Vital signs (to include blood pressure [BP], heart rate [HR], respiratory rate [RR], and body temperature).
- Height and weight. Length will be measured if height cannot be obtained.
- Physical, neurological, and developmental examination (developmental examination is limited to pediatric patients 2 to 17 years of age, inclusive)
- Clinical laboratory tests (chemistry and hematology)
- Urinalysis (an attempt should be made to collect a urine sample at this screening visit. Otherwise, the urine sample can be collected at baseline.)
- Drug screen (plasma) for THC and CBD. If the screening drug test is positive, the patient can be retested after two weeks.
- Serum pregnancy test for all girls/women of childbearing potential
- Tanner staging
- Concomitant AED review and levels if per standard of care
- [REDACTED]
- AEs
- Seizure and medication diary set up and review. Caregiver given seizure diary and instructions for use.

A screen failure is a patient for whom informed consent/assent has been obtained and has failed to meet the inclusion criteria and/or met at least one of the exclusion criteria and has not been administered the IP.

Patient rescreening is allowed as agreed by the sponsor and the investigator unless there is a general concern for patient safety or an inability for the patient to become eligible (e.g., GNX allergy, sensitivity or exposure, non-TSC and/or other ineligible epilepsy, chronic prohibited medical condition or treatment). Subsequent screening should take place at least 30 days from the patient's last visit.

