3 DATA HANDLING CONVENTIONS

3.1 DERIVED AND TRANSFORMED DATA

3.1.1 Baseline Definition

The Baseline Visit is defined as Visit 2 (Week/Day 0). Baseline values for non-seizure efficacy and safety assessments will be the last values collected prior to the first administration of IP (i.e., GNX), unless otherwise specified.

Baseline seizure frequency data is collected during the four weeks between the Screening Visit (Visit 1, Week -4) and the Baseline Visit (Visit 2, Day 0). This interval may range from no less than 28 days to no more than 32 days.

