3.1.3 Derivations

3.1.3.1 Baseline seizure frequency

Baseline 28-day seizure frequency will be calculated as the total number of primary seizures in the baseline period, i.e. between screening (Visit 1, Week -4) and baseline treatment (Visit 2, Week/Day 0), divided by the number of days with non-missing seizure data in the baseline period, multiplied by 28.

$$\text{Baseline seizure frequency} = \frac{\text{\# seizures, baseline period}}{\text{\# baseline period days with seizure data}} \times 28$$

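### A patient who misses the 8-seizure baseline count may be rescreened, and only the passing month then serves as baseline; the bias in such patients is clear, its effect on the whole trial modest

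*Protocol*

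**What the plan says.** The rescreening rule stands in the Protocol synopsis (Methodology), Section 3.1, Table 1 footnote a and Section 7.2.1.1: "Patient rescreening is allowed as agreed by the sponsor and the investigator unless there is a general concern for patient safety or an inability" on the patient's part to meet the criteria. The examples of inability are drug allergy, sensitivity or exposure, an ineligible epilepsy, and a chronic prohibited condition or treatment. On timing, the synopsis says: "Subsequent screening should take place at least 30 days from the patient's last visit, unless otherwise noted". No maximum number of attempts is given.

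Protocol 7.2.1.1 defines the group concerned: "A screen failure is a patient for whom informed consent/assent has been obtained and has failed to meet the inclusion criteria" or has met an exclusion criterion, and has not been dosed. One inclusion criterion is the count in Protocol 4.1, item 5: "Have at least 8 countable/witnessed primary seizures during the 4-week baseline period", with seizures in at least 3 of the 4 weeks.

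SAP 3.1.1 fixes the baseline window: "Baseline seizure frequency data is collected during the four weeks between the Screening Visit (Visit 1, Week -4) and the Baseline Visit". It adds: "This interval may range from no less than 28 days to no more than 32 days". SAP 3.1.3.1 builds the denominator from this: "total number of primary seizures in the baseline period, i.e. between screening (Visit 1, Week -4) and baseline treatment (Visit 2, Week/Day 0").

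The only sensitivity analysis of the primary endpoint is a repeat in the per-protocol population (SAP 4.2.1.2), and no subgroups are planned (SAP 2.5). SAP 4.1.1 summarises the number of screen failures and lists their reasons. It does not identify treated patients who had failed an earlier screening.

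**The concern.** The month that decides entry is also the denominator of the primary endpoint. A patient whose usual rate lies near or below 8 enters only in a month that happens to be high. On return to the usual rate the patient appears improved, whatever the drug does.

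Rescreening adds to this in two ways. It brings in patients with lower true rates, and it leaves out a prospectively recorded month already known to be low. The trial has one arm, so no comparison group absorbs the regression to the mean. The same denominator feeds the 50% responder rate and the 35% reduction required for Part B.

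**Working it through.** **1. Does the text permit it?** Failing the count is failing an inclusion criterion, so the patient is a screen failure (7.2.1.1). A low count can change the next month, unlike the listed examples of inability. Return is therefore allowed by agreement after 30 days. The baseline interval is at most 32 days, so it cannot contain a month that ended at least 30 days before the new screening visit. The earlier month is left out.

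**2. The plan's own figures.** The sample size (36 screened, 30 enrolled; Protocol 9.4) was not derived statistically, and no seizure rate or variance is given. There is nothing to reproduce, and every size below rests on assumptions.

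**3. One fixed rate by hand.** Assume a true rate of 6 per 28 days, Poisson counts and no drug effect.
- P(X ≥ 8) = 0.256. The 3-of-4-weeks rule brings this to about 0.25.
- Chance of qualifying within two attempts: 1 - 0.75² = 0.44.
- Mean qualifying baseline: 6 × P(X ≥ 7) / P(X ≥ 8) = 6 × 0.394 / 0.256 = 9.2.
- Ratio of means: 6 / 9.2 - 1 = -35%. The mean of individual percent changes, by simulation, is -34%.

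This fall is the same on a first or second attempt. It belongs to the floor of 8. Rescreening raises the share of such patients who get in, from 25% to 44%. The effect fades at higher rates: the median change is -19% at a rate of 8, -8% at 10 and 0% at 15.

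**4. A mixed population, no drug effect.** Assumptions: true 28-day rates lognormal with median 15 or 25 and log-SD 1; month-to-month gamma variation with shape 3, 5, 10 or none (eight scenarios, 300,000 patients each); criterion 5 applied in full; every failure rescreened once; 12 weeks after baseline; no missing diary days.

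| Quantity | Range over the eight scenarios |
|---|---|
| Median change, first-attempt qualifiers | -1% to -11% |
| Median change, rescreened qualifiers | -20% to -29% |
| Rescreened patients with a fall of at least 50% | 11% to 30% |
| First-attempt patients with a fall of at least 50% | 1% to 19% |
| Rescreened patients meeting the 35% Part B rule | 27% to 45% |
| Rescreened share of those enrolled | 4% to 16% |
| Shift in trial median | 0.6 to 3.4 points towards benefit |
| Shift in 50% responder rate | 0.4 to 1.7 points |
| Shift in share meeting the 35% rule | 1 to 2.2 points |

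In 30 patients, 1.7 points is 0.017 × 30 = 0.5 patient and 2.2 points is 0.7 patient.

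**5. A wider grid.** Over 24 scenarios (median rate 8, 12, 20 or 40; log-SD 0.8 or 1.0; Poisson, or gamma-Poisson with k = 4 or 2) the rescreened median is -13% to -41%. First-attempt qualifiers range from +2% to -29%. Rescreened patients are 1% to 28% of those enrolled, and the trial median moves 0 to 4 points.

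**6. Check against the recruitment plan.** With 36 screened and 30 enrolled, 6 are never enrolled. Suppose all 6 are count failures who also failed a second attempt, and let p be the chance of passing that attempt. First failures number 6/(1 - p), so rescreened entrants number 6p/(1 - p): 2 at p = 0.25, 4 at p = 0.4 and 6 at p = 0.5. The eight scenarios give p of 0.24 to 0.47, hence 1.9 to 5.3 entrants. This is an upper figure, because some of the 6 will be lost for other reasons.

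**The case against.** No sentence says that patients who fail the count will be rescreened. Each rescreening needs sponsor and investigator agreement, and inclusion criterion 6 adds sponsor or designee approval. The trial is a descriptive proof of concept, the Part B rule already has a sponsor-approved exception, and reasons for screen failure will be listed. All of this stands and limits the weight of the point. It does not remove it: no criterion steers the agreement away from low-count failures, and nothing planned shows how many treated patients entered this way.

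A reader might infer more than the documents support:
- **Repeated attempts until a month succeeds.** No cap is stated, but no passage describes serial retries either, and each would need fresh agreement.
- **A large shift in the trial result**, for example from 6 of 30 patients entering by rescreening. That is 20% of those enrolled. The eight scenarios give 4% to 16% even with universal rescreening.
- **An apparent benefit in the trial mean.** Percent change is right-skewed. With rescreened patients included, the no-effect mean is still above zero in 7 of the 8 scenarios (-1.5% to +20.5%). The median is the clearer measure here.
- **That the -34% at a rate of 6 is caused by rescreening.** It comes from the floor and applies equally to first-attempt qualifiers.

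**Conclusion.** The point holds at modest size. The text permits rescreening after a failed count and confines the baseline to the passing month, and no analysis separates these patients. With no drug effect they show a median fall about 19 points deeper than first-attempt qualifiers at either end of the range (-20% against -1%, -29% against -11%).

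The trial-level effect is small: at most about 3.4 points on the median in the eight scenarios (4 in the wider grid), and less than one patient in 30 on the responder and 35% measures. It would be nil if no such patient is enrolled. The direction is known; the size depends on seizure rates, variability and the number rescreened, none of which the documents give. This supports a cheap improvement. It does not support a claim that the primary result is invalid.

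**What to change.** **Protocol** (synopsis, 3.1, Table 1 footnote a, 7.2.1.1): add failure of the 8-seizure count to the reasons for which rescreening is not allowed. Leave failure on weekly spread alone outside the bar. Such a patient did reach 8 seizures, so the next month is not a selected high one, and these were under 1% of simulated failures.

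**SAP**, if any such patient has been enrolled: report the number in the disposition summary (4.1.1), and add to 4.2.1.2 a repeat of the primary and 50% responder summaries without them. This needs only a flag for earlier count failure. It does not depend on the failed-month diary being held in the analysis database, which no passage promises.

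Do not substitute a baseline pooled over failed and passing months. The failed month is itself selected low, so pooling tends to over-correct: the no-effect median becomes 0% to +17% in the eight scenarios and -7% to +44% in the wider grid.

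**Cost:** one protocol clause, one SAP sentence, one extra table, and a few low-count candidates lost to recruitment. The fall in first-attempt qualifiers remains and should be kept in mind when the primary result is read.

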**Pharmacokinetic Assessments:**

The pharmacokinetic (PK) population will include all patients who have received at least 1 dose of GNX and who have had at least 1 sample collected and a valid bioanalytical result obtained. The samples will be drawn between 1 and 5 hours or between 4 and 8 hours after the last dose during Part A and Part B. Pharmacokinetic analyses will be limited to listing of concentrations because sufficient concentration-time data will not be available for noncompartmental analyses such as maximum plasma concentration (C_{max}), area under the concentration versus time curve (AUC), or time of maximum concentration (t_{max}). Pharmacokinetic data from this study may be used for a Population PK analyses to be conducted separately from this study and reported separately. Further details will be provided in the Statistical Analysis Plan.

Safety and Tolerability Assessments:

Safety and tolerability will be assessed by monitoring vital signs (blood pressure [BP], heart rate [HR], respiratory rate [RR], body temperature, electrocardiograms (ECGs), clinical laboratory tests (hematology, chemistry and urinalysis), physical, neurological, and developmental examinations, Columbia-Suicide Severity Rating Scale (C-SSRS) if appropriate and frequency, type, and severity of adverse events (AEs) during Part A and Part B. Height and weight will also be measured.

Statistical Methods:

The intent-to-treat (ITT) population comprises all patients who received at least one dose of IP. The ITT population will be the primary population for efficacy analyses. The Per-Protocol (PP) population includes all ITT patients without major protocol violations (defined prior to database lock). Safety will be reported in all patients.

Since this is an OL proof of concept study, no inferential statistical testing will be conducted, and all efficacy outcomes will be descriptive.

Primary Endpoint: Definition and Analysis:

The primary efficacy endpoint (change in seizure frequency) is the percent change in 28-day seizure frequency through the end of the 12-week treatment period (4-week titration and 8-week maintenance) relative to the baseline, based on the primary seizure types. The primary seizure types are defined as the following: focal motor seizures without impairment of consciousness or awareness, focal seizures with impairment of consciousness or awareness, focal seizures evolving to bilateral, tonic-clonic convulsive seizures, and generalized motor seizures including tonic-clonic, bilateral tonic, bilateral clonic, or atonic/drop seizures. Focal aware non-motor and generalized seizures without motor features, infantile or epileptic spasms, and myoclonic seizures do not count as the primary seizure types.

Post-baseline 28-day seizure frequency will be calculated as the total number of seizures in the 12-week treatment periods (4-week titration plus 8-week maintenance period) during Part A divided by the number of days with seizure data in the period, multiplied by 28. Baseline 28-day seizure frequency will be calculated as the total number of primary seizures in the baseline period divided by the number of days with seizure data in the baseline period, multiplied by 28.

$$\left(\frac{[(\text{Post-baseline 28-day seizure frequency}) - (\text{Baseline 28-day seizure frequency})]}{(\text{Baseline 28-day seizure frequency})} \right) \times 100\%$$

The baseline, post-baseline, and arithmetic and percent changes from baseline in 28-day seizure frequency will be summarized using descriptive statistics.

Since this is an OL proof of concept study, all efficacy analyses will be based on descriptive statistics.

Sample Size:

Since this is an OL proof of concept study, sample size was not determined by statistical methods.

Secondary and Exploratory Endpoints - Descriptive Evaluation:**Seizure control:**

- Percentage of patients experiencing a $\geq 50\%$ reduction in 28-day primary seizure frequency through the end of the 12-week treatment period compared to the 4-week Baseline Period.

Other:

- CGI-I, parent/caregiver and clinician.
- CGI-C - Target Behavior.

Exploratory Endpoints - Descriptive Evaluation:

All secondary and

IND 044,020
Protocol 1042-TSC-2001Marinus Pharmaceuticals, Inc.
11 Jun 2021

[REDACTED]
 
[REDACTED]


Safety Analysis: Safety will be reported for all patients. The results in Part A and Part B will be summarized separately and then the combined results in Part A and Part B will be summarized together. Adverse events will be tabulated by overall, system organ class, and Preferred Term using the Medical Dictionary for Regulatory Activities (MedDRA) coding system. Incidence and percentage of AEs will be presented. Additional tables, with AEs classified by severity and by only those related to drug as assessed by the investigator will be presented. Subset listings will be produced for AEs that cause withdrawal and for serious adverse events (SAEs). Clinical laboratory tests (hematology, chemistry and urinalysis), vital signs (temperature, BP, pulse rate), weight, and ECGs will be summarized using descriptive statistics including changes from baseline. Change in C-SSRS scores where applicable will be determined. Physical, neurological and developmental examinations will be summarized using number and percentage of patients with abnormalities.

Pharmacokinetic Analysis: A population PK approach addressing the relationship between GNX PK parameters and individual characteristics will be implemented during the study. One blood sample will be obtained at the following visits for PK analyses:
 
• During Part A:
- Visit 4 (Week 5): between 1 and 5 hours since the last IP dosing- Visit 5 (Week 12): between 4 and 8 hours since the last IP dosing• During Part B: There is no specified time to draw the PK sample and can be drawn when convenient during the study visits. 
Exact time of sample withdrawal and drug intake will be recorded in the electronic case report form (eCRF).

[REDACTED] and Concomitant AED levels: Blood samples will be drawn at screening visit, [REDACTED]
 
[REDACTED] Concomitant AED levels will not be mandatory but will be conducted per sites' standard of care. If AED levels are available, the results, date and time of last AED dose and date and time of AED PK sample will be recorded in the eCRF. [REDACTED] and concomitant AED levels will be analyzed according to the SAP.

Interim Analysis: No formal interim analysis is planned.

Table 1: Schedule of Assessments - Part A

WEEK	Part A										
	Screen/Baseline		Titration and Maintenance								
-4 (Screening Visit – Start of Baseline)	0 (Baseline Treatment Visit)	Day 1	Day 2	Day 3	1	2, 3, 4	5	9	12	16 Taper/Safety Visits ^p	
Visit Windows	+ 4 days		± 1 day		± 3 days	± 3 days	± 3 days	± 3 days	± 3 days	± 3 days	
VISIT	Visit 1 ^a	Visit 2 ^o	Phone Follow-up	Phone Follow-up	Phone Follow-up	Visit 3	Phone Follow-up	Visit 4	Phone Follow-up	Visit 5	Visit 5a
Informed Consent ^b	X										
Demographics & Medical History	X	X ^s									
Inclusion/Exclusion Criteria	X	X									
Genetic testing	X ^c	X ^r									
Seizure Identification and Diagnostic Review Form (Epilepsy Study Consortium)	X	X									
Vital Signs (BP, HR, RR, and body temperature)	X	X			X		X		X		X
Height / weight	X ^d	X ^e			X ^e		X ^e		X ^e		
Physical/Neurological/Developmental Exam ^t	X	X			X		X		X		
ECG		X			X		X		X		
Clinical Laboratory Tests ^f	X	X			X		X		X		
Urinalysis	X ^g	X ^g			X		X		X		
Drug Screen ^h	X	X							X		
Pregnancy Test (WCBP) ⁱ	X	X					X		X		

Table 1: Schedule of Assessments - Part A

WEEK	Part A										
	Screen/Baseline		Titration and Maintenance								
-4 (Screening Visit – Start of Baseline)	0 (Baseline Treatment Visit)	Day 1	Day 2	Day 3	1	2, 3, 4	5	9	12	16 Taper/Safety Visits ^p	
Visit Windows	+ 4 days		± 1 day		± 3 days	± 3 days	± 3 days	± 3 days	± 3 days	± 3 days	
VISIT	Visit 1 ^a	Visit 2 ^o	Phone Follow-up	Phone Follow-up	Phone Follow-up	Visit 3	Phone Follow-up	Visit 4	Phone Follow-up	Visit 5	Visit 5a
Tanner Staging	X										X
IP PK							X ^j		X ^j		
Concomitant AED Review and Levels if Per Standard of Care ^k	X	X			X		X		X		
Adverse Event	X	X	X	X	X	X	X	X	X		X
Seizure and Medication Diary Review ^l	X ^l	X	X	X	X	X	X	X	X		X
CGI-C - Target Behavior		X ^m					X		X		
CGI-I (caregiver)		X					X		X		
CGI-I (clinician)		X					X		X		
C-SSRS (baseline form) ^q		X									
C-SSRS (since previous visit) ^q							X		X		X
Dispense GNX ⁿ		X					X		X		

AED = antiepileptic drug, BP = blood pressure, CBD = cannabidiol, CGI-C = Caregiver Global Impression of Change, CGI-I = Clinical Global Impression – Improvement, C-SSRS = Columbia-Suicide Severity Rating Scale, D/C = discontinuation, ECG = electrocardiogram, [REDACTED], GNX = ganaxolone, HR = heart rate, IP = investigational product, LAR = legally authorized representative, PK = pharmacokinetic, RR = respiratory rate, THC = tetrahydrocannabinol, WCBP = women of childbearing potential.

Table 1: Schedule of Assessments - Part A

WEEK	Part A										
	Screen/Baseline		Titration and Maintenance								
-4 (Screening Visit – Start of Baseline)	0 (Baseline Treatment Visit)	Day 1	Day 2	Day 3	1	2, 3, 4	5	9	12	16 Taper/Safety Visits ^p	
Visit Windows	+ 4 days			± 1 day	± 3 days	± 3 days	± 3 days	± 3 days	± 3 days	± 3 days	
VISIT	Visit 1 ^a	Visit 2 ^o	Phone Follow-up	Phone Follow-up	Phone Follow-up	Visit 3	Phone Follow-up	Visit 4	Phone Follow-up	Visit 5	Visit 5a
a.	Patient rescreening is allowed as agreed by the sponsor and the investigator unless there is a general concern for patient safety or an inability for the patient to become eligible (e.g., GNX allergy, sensitivity or exposure, non-TSC and/or other ineligible epilepsy, chronic prohibited medical condition or treatment). Subsequent screening should take place at least 30 days from the patient's last visit.										
b.	Written informed consent/assent must be obtained from patient, parent or LAR before any study assessments are performed. Pediatric assent should be obtained, if appropriate.										
c.	Previous genetic testing results will be accepted and reviewed to assess if a pathogenic TSC1 or TSC2 variant is present. If genetic testing has not previously been performed, then a biological sample will be obtained to complete genetic testing at the sponsor's designated lab. Note: TSC diagnosis does not require pathogenic TSC1 or TSC2 mutations if the clinical criteria are met.										
d.	Height and weight will be measured. Length will be measured if height cannot be obtained.										
e.	Only weight will be measured. At each visit, dosing will be reviewed and adjusted as needed based on a patient's current weight.										
f.	Chemistry and Hematology.										
g.	An attempt should be made to collect a urine sample for a urinalysis at screening; otherwise, the urine sample can be collected at baseline for the urinalysis if possible.										
h.	A drug screen (plasma) will be performed to test for THC and CBD at screening. If the screening drug test is positive, the patient can be retested, via plasma, after two weeks. A positive drug test during the treatment period will result in early termination.										
i.	Serum pregnancy test is required for all girls/women of childbearing potential.										
j.	Population PK will be conducted at these visits (Visit 4: between 1-5 hours since last IP dosing, Visit 5: between 4-8 hours since the last IP dosing).										
k.	Concomitant AEDs or their dose must be stable for 1 month prior to screening and cannot be changed at any time prior to Visit 4, but may be adjusted during Part B.										
l.	Caregiver given seizure and medication diary and instructions for use.										
m.	During the baseline visit, the investigator and parent/caregiver/LAR will decide on a domain and identify the specific behavior that the patient exhibits that denotes the domain. This behavior will be used at subsequent visits to assess change after the initiation of IP.										
n.	Patients who discontinue IP early will be encouraged to continue with all procedures and scheduled visits.										
o.	The 4 weeks between Screening Visit and Baseline Treatment Visit can be no less than 28 days and no more than 32 days.										
p.	Only for patients who do not continue into Part B. This will occur after 2 weeks of taper and 2 weeks after completion of treatment.										
q.	Only for patients \geq 7 years old if appropriate. Otherwise clinical judgment will be used.										
r.	Only for patients that were Screened without previous genetic testing results and had a genetic test performed at the sponsor's designated lab.										

Table 1: Schedule of Assessments - Part A

WEEK	Part A										
	Screen/Baseline		Titration and Maintenance								
-4 (Screening Visit – Start of Baseline)	0 (Baseline Treatment Visit)	Day 1	Day 2	Day 3	1	2, 3, 4	5	9	12	16 Taper/Safety Visits ^p	
Visit Windows	+ 4 days			± 1 day	± 3 days	± 3 days	± 3 days	± 3 days	± 3 days	± 3 days	
VISIT	Visit 1 ^a	Visit 2 ^o	Phone Follow-up	Phone Follow-up	Phone Follow-up	Visit 3	Phone Follow-up	Visit 4	Phone Follow-up	Visit 5	Visit 5a

s. Review of medical history only.

t. Developmental examination is limited to pediatric patients 2 to 17 years of age, inclusive.

Table 2: Schedule of Assessments - Part B

Part B								
	Final Part A Visit/ First Part B Visit	Open-Label Extension (Visits will be every 8 weeks with a telephone follow-up in-between)					Final OLE Visit or Taper Visit	Safety Follow-up Post-taper
WEEK	12	16	20	24	28	32	36 or early D/C	2 weeks post last dose
Visit Windows		± 7 days	± 7 days	± 7 days	± 7 days	± 7 days	± 7 days	± 3 days
VISIT	Visit 5	Phone follow-up	Visit 6	Phone follow-up	Visit 7	Phone follow-up	Visit 8 (Week 36) ^g or Visit X (early D/C)	Visit X
Confirm patient is “OLE eligible” (≥ 35% reduction in seizure frequency)	X							
Vital signs (BP, HR, RR, and body temperature)	X		X		X		X	X
Weight ^a	X		X		X		X	
Physical/Neurological/Developmental Exam	X		X		X		X	X
ECG	X				X		X ^d	
Clinical Laboratory Tests ^b	X		X		X		X	X
Urinalysis	X				X		X	X
Drug Screen	X				X			
Pregnancy Test (WCBP) ^c	X		X		X		X	X
Tanner Staging							X ^d	
IP PK ^e	X		X		X		X	X
Concomitant AED Review and levels if per standard of care	X		X		X		X	X

Table 2: Schedule of Assessments - Part B

		Part B							
		Final Part A Visit/ First Part B Visit	Open-Label Extension (Visits will be every 8 weeks with a telephone follow-up in-between)					Final OLE Visit or Taper Visit	Safety Follow-up Post-taper
WEEK		12	16	20	24	28	32	36 or early D/C	2 weeks post last dose
Visit Windows			± 7 days	± 7 days	± 7 days	± 7 days	± 7 days	± 7 days	± 3 days
VISIT		Visit 5	Phone follow-up	Visit 6	Phone follow-up	Visit 7	Phone follow-up	Visit 8 (Week 36) ^g or Visit X (early D/C)	Visit X
[REDACTED]		[REDACTED]						[REDACTED]	
Adverse Event		X	X	X	X	X	X	X	X
Seizure and Medication Diary Review		X	X	X	X	X	X	X	X
[REDACTED]		[REDACTED]						[REDACTED]	
CGI-C - Target Behavior		X						X	
CGI-I (caregiver)		X						X	
CGI-I (clinician)		X						X	
C-SSRS (since last visit form) ^f		X		X		X		X	
Dispense GNX		X		X		X		X	

AED = antiepileptic drug, BP = blood pressure, CGI-C = Caregiver Global Impression of Change, CGI-I = Clinical Global Impression – Improvement, C-SSRS = Columbia-Suicide Severity Rating Scale, D/C = discontinuation, ECG = electrocardiogram, [REDACTED], GNX = ganaxolone, HR = heart rate, IP = investigational product, OLE = open-label extension, PK = pharmacokinetic, RR = respiratory rate, WCBP = women of childbearing potential.

- Weight will be measured at every visit, except the safety follow-up visit.
- Chemistry and Hematology.
- Serum pregnancy test is required for all girls/women of childbearing potential.
- Conduct at Week 36/Visit 8 or the last open-label extension visit if prior to Week 36/Visit 8.
- PK samples can be drawn when convenient during the study visits.

Table 2: Schedule of Assessments - Part B

Part B									
	Final Part A Visit/ First Part B Visit	Open-Label Extension (Visits will be every 8 weeks with a telephone follow-up in-between)						Final OLE Visit or Taper Visit	Safety Follow-up Post-taper
WEEK	12	16	20	24	28	32	36 or early D/C	2 weeks post last dose	
Visit Windows		± 7 days	± 7 days	± 7 days	± 7 days	± 7 days	± 7 days	± 3 days	
VISIT	Visit 5	Phone follow-up	Visit 6	Phone follow-up	Visit 7	Phone follow-up	Visit 8 (Week 36) ^g or Visit X (early D/C)	Visit X	
f.	Only for patients \geq 7 years old if appropriate. Otherwise clinical judgment will be used.								
g.	Consistent with V8 (Week 36) or Visit X, patients can be seen at Investigator's discretion for unscheduled visits.								

